6.7. Previous and Concomitant Medications

Summaries of previous and concomitant medications used for RA including cDMARDs (MTX only, MTX and other cDMARDs; see Section 6.6) will be based on the safety population.

At screening, medications used for RA that had been previously discontinued are recorded for each patient. A summary of previous medications used for RA will be prepared using frequency counts and percentages by World Health Organization (WHO) drug anatomical therapeutic chemical (ATC) classification and treatment group.

Concomitant therapy will be recorded at each visit and will be classified according to the WHO drug dictionary and summarized using frequency counts and percentages by WHO drug ATC classification sorted by decreasing frequency and treatment group.

Concomitant medications are defined as:

- Concomitant medications with a stop date on or after the date of the first dose of the study drug and that precedes Week 24 (Visit 11) or an early discontinuation visit prior to Week 24 will be included in the concomitant medications summaries for the analysis at the end of Part A. Should there be insufficient data to make this comparison (for example, the concomitant therapy stop year is the same as the treatment start year, but the concomitant therapy stop month and day are missing), the medication will be considered as concomitant for Part A.

- For patients who continue in Part B, concomitant medications with a stop date that is after Week 24 or ongoing will be included in the concomitant medications summaries at the end of Part B.

Summaries of concomitant medications will be provided using data up to rescue/switch for the following categories:

- concomitant medications used for RA
- concomitant medications excluding RA and statin therapies
- concomitant medications - statins

Concomitant therapies will also be summarized for the all baricitinib exposures group including data after rescue/switch.

6.8. Historical Diagnoses and Pre-Existing Conditions

The number and percentage of patients with selected historical diagnoses, as listed on the eCRF, will be summarized by treatment group using the mITT population. Historical diagnoses will be identified using the Medical Dictionary for Regulatory Activities (MedDRA®, most current available version) algorithmic standardized MedDRA queries (SMQs) or similar Lilly-defined lists of preferred terms (PTs) of interest.

Pre-existing conditions are defined as those conditions recorded on the Pre-existing Conditions and AEs eCRF page with a start date prior to the date of informed consent. Note that conditions with a partial or missing start date will be assumed to be 'not pre-existing' unless there is evidence, through comparison of partial dates, to suggest otherwise. Pre-existing conditions will be identified using the MedDRA SMQs or similar Lilly-defined lists of PTs of interest.

Frequency counts and percentages of patients with selected pre-existing conditions will be summarized by treatment group using the mITT population.

6.9. Treatment Compliance

Patient compliance with study medication will be assessed from randomization visit (Week 0) to Visit 15 (Week 52) during the treatment period. Compliance will be summarized by treatment groups from randomization to visit of rescue/switch using the mITT population.

All patients are expected to be taking 1 tablet of baricitinib or baricitinib placebo daily in Parts A and B regardless of rescue; a patient is considered significantly noncompliant if he or she misses >20% of the prescribed doses during the study. Similarly, a patient will be considered significantly noncompliant if he or she is judged by the investigator to have intentionally or repeatedly taken more than the prescribed amount of study drug. For patients who have their dose interrupted because of safety reasons, the period of dose withholding will be taken into account in the compliance calculation as outlined below.

Compliance to baricitinib and baricitinib placebo in the period of interest will be calculated as follows:

$$\frac{\text{actual total # of tablets used}}{\text{Expected total # of tablets used}} \times 100$$

Where:

the expected total # tablets used = the number of days in the period of interest;

the actual total # of tablets used = total number dispensed – total number returned in the period.

If a patient has dose interrupted for safety reasons during the period, the total number of days drug was withheld will be deducted from the expected total # of tablets used.

Patients who are significantly noncompliant in Part A will be excluded from the PP population.

The summary statistics of percent compliance and non-compliance rate will be summarized by treatment group. The sub-total percent compliance for Weeks 0 through 12, the sub-total percent compliance for Weeks 0 through 24, and grand-total percent compliance for Weeks 0 through 52 with data up to the time of rescue/switch will be presented, as well, along with the associated non-compliance rates. The number of expected doses, tablets dispensed, tablets returned, and percent compliance will be listed by patient.

6.10. Treatment Exposure

Duration of exposure to each study drug will be summarized for the safety population using descriptive statistics (n, mean, SD, minimum, median, maximum). Cumulative exposure and duration of exposure will be summarized in terms of frequency counts and percentages by category and treatment group.

Overall exposure will be summarized in total patient-years which are calculated according to the following:

Exposure in patient-years = sum of duration of exposure in days (for all patients in treatment group) / 365.25.

The summary for the first database lock (end of Part A) will include exposure to each treatment plus exposure for the subset of patients who are rescued during Part A from each randomized therapy.

The summary for the final lock (end of Parts A and B) will include all exposures for patients randomized to baricitinib and placebo, plus all exposures subsequent to rescue or switch to baricitinib. For the baricitinib treatment group, exposure will be calculated including the subset of patients who are rescued.

Duration of exposure will be calculated as follows:

1. Baricitinib group:

- Duration of exposure to baricitinib excluding exposure after the initiation of rescue therapy will be calculated as: [date of last study drug treatment prior to rescue – date of first study drug dose (Visit 2) + 1].
- Duration of exposure to baricitinib after the initiation of rescue therapy will be calculated as: (date of last study drug treatment – date of first baricitinib dose as rescue therapy + 1).

2. Placebo group:

- Duration of exposure to placebo excluding exposure after the initiation of rescue therapy will be calculated as: [date of last study drug treatment prior to rescue – date of first study drug dose (Visit 2) + 1].
- Duration of exposure to baricitinib after the initiation of rescue therapy will be calculated as: [date of last study drug treatment – date of first baricitinib dose as rescue therapy + 1].
- Duration of exposure to baricitinib after switch will be calculated as: (date of last study drug treatment (before rescue, if applicable) – date of first dose of study drug after switch + 1).

Summaries of treatment exposure will also include all baricitinib exposures.

6.11. Efficacy Analyses

Efficacy analyses will use the mITT population defined in Section 6.1.3 and will generally be analyzed according to the following 2 formats:

- Week 0 (Visit 2) to Week 52 (Visit 15) with data included up to the time of rescue/switch. Formal statistical tests will be used to compare the baricitinib group to the placebo group for these efficacy outcomes through Week 24;
- Week 0 (Visit 2) to Week 52 (Visit 15) for rescued/switched patients with data included after rescue/switch. These efficacy results will be summarized by treatment group, but no formal statistical comparisons will be performed.

6.11.1. Primary Outcome and Methodology

The primary efficacy measure will be the proportion of patients achieving ACR20 at Week 12 based on the change in ACR response values from baseline. ACR20 is defined as at least 20% improvement from baseline in the following ACR Core Set variables:

- TJC68
- SJC66
- An improvement of $\geq 20\%$ from baseline in at least 3 of the following 5 assessments:
 - Patient's assessment of pain (VAS)
 - Patient's Global Assessment of Disease Activity (VAS)
 - Physician's Global Assessment of Disease Activity (VAS)
 - Patient's assessment of physical function as measured by the HAQ-DI
 - Acute phase reactant as measured by hsCRP

Refer to the algorithm to calculate ACR response in [Appendix 1](#).

The primary efficacy analysis compares ACR20 at Week 12 between baricitinib and placebo using the mITT population. The PP population results will be used as supportive to the mITT results. A logistic regression model with treatment, country/region, and joint erosion status (1-2 joint erosions plus seropositivity versus at least 3 joint erosions) in the model will be used to test the treatment difference between baricitinib and placebo in the proportion of patients achieving ACR20 response at Week 12 using the Wald test at 2-sided significance level of 0.05. The NRI approach will be used to impute response status for patients with completely missing data. The p-value and 95% CI of odds ratio from the logistic regression model will be reported. The 95%

CI of responder rate difference will be calculated using the Newcombe-Wilson method (Newcombe 1998) without continuity correction. Treatment-by-country/region interaction will be added to the logistic regression model as a sensitivity analysis and results from this model will be compared to the primary model. If the treatment-by-country/region interaction is significant at a 2-sided 0.1-alpha level, the nature of this interaction will be inspected as to whether it is quantitative (ie, the treatment effect is consistent in direction but not size of effect) or qualitative (the treatment is beneficial in some but not all countries). If the treatment-by-country/region interaction effect is found to be quantitative, results from the primary model will be presented. If the treatment-by-country/region interaction effect is found to be qualitative, further inspection will be used to identify in which countries baricitinib is found to be more beneficial.

6.11.2. Secondary Efficacy Analyses

Unless otherwise stated, the following analyses will be performed to test for superiority of baricitinib relative to the placebo group.

The secondary efficacy measures are:

- Change from baseline to Week 12 in HAQ-DI score
- Change from baseline to Week 12 in DAS28-hsCRP
- Proportion of patients achieving an SDAI score ≤ 3.3 at Week 12
- Mean duration of morning joint stiffness (paper diary; 7 days prior to Week 12)
- Mean severity of morning joint stiffness (paper diary; 7 days prior to Week 12)
- Mean “Worst Tiredness” NRS (paper diary; 7 days prior to Week 12)
- Mean “Worst Joint Pain” NRS (paper diary; 7 days prior to Week 12)

The secondary efficacy measures will be analyzed using the mITT population. The PP population results will be used as supportive to the mITT results. These analyses are described as follows:

- **Comparison between baricitinib and placebo in change from baseline to Week 12 in HAQ-DI score and in DAS28-hsCRP:** an ANCOVA model with baseline score, country/region, joint erosion status, and treatment group in the model will be used to test the treatment difference between baricitinib and placebo in change from baseline to Week 12 in HAQ-DI and in DAS28-hsCRP. Type III sums of squares for the LS means will be used for the statistical comparison; 95% CI will also be reported. The LS mean difference, SE, CI, and p-value will be presented. The mBOCF approach described in Section 6.3.1 will be used to impute missing data.
- **Comparison between baricitinib and placebo in proportion of patients achieving an SDAI score ≤ 3.3 at Week 12:** A logistic regression model with treatment, country/region, and joint erosion status in the model will be used to test the treatment difference between baricitinib and placebo in the proportion of patients achieving an SDAI score ≤ 3.3 at Week 12. The NRI method as described in Section 6.3.1 will be used to impute missing data. The p-value and 95% CI of odds ratio from the logistic regression model will be reported for statistical inference. The 95% CI of responder rate difference will be calculated using the Newcombe-Wilson method (Newcombe 1998) without continuity correction.

- **Comparison between baricitinib and placebo in mean duration of morning joint stiffness in the 7 days prior to Week 12:** refer to Section 6.13 for the statistical methods used for the analysis of mean duration of morning joint stiffness.
- **Comparison between baricitinib and placebo in mean severity of morning joint stiffness in the 7 days prior to Week 12:** refer to Section 6.13 for the statistical methods used for the analysis of severity of morning joint stiffness.
- **Comparison between baricitinib and placebo in mean “Worst Tiredness” NRS in the 7 days prior to Week 12:** refer to Section 6.13 for the statistical methods used for the analysis of “worst tiredness.”
- **Comparison between baricitinib and placebo in mean “Worst Joint Pain” NRS in the 7 days prior to Week 12:** refer to Section 6.13 for the statistical methods used for the analysis of “worst joint pain.”

6.11.3. *Efficacy Analyses in Follow-Up Period*

Summaries of efficacy data collected during the post-treatment follow-up period (Part C) will be presented separately from the main summaries (Parts A and B). The efficacy measures to be summarized include DAS28-hsCRP, DAS28-ESR, ACR component scores (TJC68, SJC66, patient’s assessment of pain, Patient’s Global Assessment of Disease Activity, Physician’s Global Assessment of Disease Activity, HAQ-DI, and hsCRP), CDAI, and SDAI. The summary statistics of these measures at study baseline, follow-up baseline, at follow-up visit, and for the changes from study baseline and from follow-up baseline to follow-up visit will be presented based on the groups defined in Section 6.1 for the follow-up population. The follow-up baseline is defined as the data collected at the last visit in Parts A and B prior to entering the follow-up period. Patients who have data for both the follow-up baseline and the follow-up visit are included in the analysis. Some other analyses for efficacy measures will be explored as well.

6.12. Pharmacokinetic/Pharmacodynamic Analysis (PK/PD)

No PK/PD samples are collected and no analyses are planned for this study.

6.13. Health Outcomes Analyses

6.13.1. Diary Data

6.13.1.1. Data Handling and Missing Data Imputation

The paper diary data (duration of morning joint stiffness, severity of morning joint stiffness, worst joint pain, worst tiredness, and recurrence of morning joint stiffness during the day) will be assessed daily from Week 0 (Visit 2) to Week 12 (Visit 7). The primary analysis is based on the scores collected in the 7 days prior to the Week 12 visit date. Similar analysis will be done for 7 days prior to each scheduled visit (Week 1, Week 2, Week 4, and Week 8) using the primary analysis method. The supportive analysis is based on daily data modeled by weekly means. The weeks are defined as follows: Day 1 on diary, Days 2-8 (Week 1), Days 9-15 (Week 2), and so on up to Days 79-85 (Week 12).

For the primary analysis, the average of the scores collected in the 7 days prior to Week 12 will be used. If there are fewer than 4 nonmissing scores, the 7-day window will be shifted back in time (toward baseline) 1 day at a time until there are 4 nonmissing scores available in the 7-day window. Then the average of the 4 scores will be used in the Week 12 analysis. This will be repeated for each scheduled visit (week 1, week 2, week 4, week 8) prior to week 12.

For patients who discontinue the study or permanently discontinue the study treatment, the scores collected in the last 7 days prior to discontinuation will be used in the analysis. If a patient undergoes a temporary interruption of study drug at the time of study database lock, this patient will be treated as having permanently discontinued from study drug in the missing data imputation. If there are fewer than 4 nonmissing scores, a similar approach will be used to find 4 nonmissing scores in a 7-day window and the average score will be used in the Week 12 analysis. Patients who do not have at least 4 scores in any postbaseline 7-day window up to Week 12 will have their Day 1 score carried forward to the endpoint for analysis. If the Day 1 value cannot be obtained, the first available postbaseline score will be used to impute the Day 1 score so that the patient can be included in the analysis.

For the analysis at each scheduled visit using the primary analysis method, the same imputation rule for the primary analysis will be used. The imputed value for missing Day 1 measures from postbaseline assessments as described in the primary analysis will not be used in the change from Day 1 analysis.

For the supportive analysis, if ≥ 4 scores during a defined week are missing, the daily scores collected in the week will not be used in the analysis as a protective measure against potentially unreliable or non-representative data.

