9.5. Selection and Timing of Doses

Each patient will receive blinded investigational product (baricitinib 4 mg or baricitinib placebo tablets orally QD) beginning on the day of Visit 2 (Week 0). Baricitinib 4-mg oral dosing will continue daily through Visit 15 (Week 52). Baricitinib placebo oral dosing will continue daily through Visit 11 (Week 24); at Visit 11 (Week 24), all patients randomized to placebo will be reassigned to baricitinib.

Oral investigational product should be taken at home at approximately the same time each day, as much as possible:

- At Visit 2 (Week 0), patients will take their investigational product in the clinic.

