10.2. Health Outcome Measures

The health outcome measures listed below will be administered. Country-specific translations of each measure will be available in this study. Items being measured using a paper diary should be completed at the end of the patient's day (typically their bedtime).

- Morning Joint Stiffness Severity Numeric Rating Scale (NRS): The Morning Joint Stiffness NRS is a patient-administered, single-item, 11-point horizontal scale anchored at 0 and 10, with 0 representing “no joint stiffness” and 10 representing “joint stiffness as bad as you can imagine.” Patients rate their morning joint stiffness each day (using a paper diary) by selecting the one number that describes their overall level of joint stiffness at the time they woke up.
- Duration of morning joint stiffness:
 - Patient diary: The duration of morning joint stiffness is a patient-administered item that allows for the patients to enter the length of time in hours and minutes that their morning joint stiffness lasted each day.
 - Electronic PRO (tablet): The duration of morning joint stiffness is a patient-administered item that allows for the patients to enter the length of time in minutes (using 15-minute increments) that their morning joint stiffness lasted on the day prior to that visit (using an electronic patient-reported outcomes [ePRO] tablet).
- Recurrence of joint stiffness: The recurrence of joint stiffness throughout the day is a patient-administered single-item question assessed each day (using a paper diary) that asks “Did you have any joint stiffness throughout today, other than when you woke up?” (Yes/No)
- Tiredness Severity Numeric Rating Scale (Worst Tiredness NRS):
 - Patient diary: The Worst Tiredness NRS is a patient-administered, single-item, 11-point horizontal scale anchored at 0 and 10, with 0 representing “no tiredness” and 10 representing “as bad as you can imagine.” Patients rate their tiredness each day (using a paper diary) by selecting the one number that describes their worst level of tiredness.

- Electronic PRO (tablet): The Worst Tiredness NRS is a patient-administered, single-item, 11-point horizontal scale anchored at 0 and 10, with 0 representing “no tiredness” and 10 representing “as bad as you can imagine.” Patients rate their tiredness by selecting the one number that describes their worst level of tiredness during the past 24 hours.
- Severity of joint pain Numeric Rating Scale (Worst Joint Pain NRS):

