12.2.7. Efficacy Analyses

Secondary analyses:

1. Comparison between baricitinib and placebo in change from baseline to Week 12 in HAQ-DI score: An ANCOVA model with treatment, country, joint erosion status, and baseline score in the model will be used to test the treatment difference between baricitinib and placebo in change from baseline to Week 12 in HAQ-DI. The mBOCF and mLOCF approaches as described above will be used to impute missing data.
2. Comparison between baricitinib and placebo in change from baseline to Week 12 in DAS28-hsCRP: An ANCOVA model with treatment, country, joint erosion status, and baseline score in the model will be used to test the treatment difference between baricitinib and placebo in change from baseline to Week 12 in DAS28-hsCRP. The mBOCF and mLOCF approaches as described above will be used to impute missing data.
3. Comparison between baricitinib and placebo in proportion of patients achieving an SDAI score ≤ 3.3 at Week 12: A logistic regression model with treatment, country, and joint erosion status in the model will be used to test the treatment difference between baricitinib and placebo in the proportion of patients achieving an SDAI score ≤ 3.3 response at Week 12. The NRI method as described above will be used to impute missing data.
4. Comparison between baricitinib and placebo in mean duration of morning joint stiffness in the 7 days prior to Week 12: An ANCOVA model with treatment, country, joint erosion status, and baseline score (Day 1 on the diaries) in the model will be used to test the treatment difference between baricitinib and placebo in mean duration of morning joint stiffness in the 7 days prior to Week 12. Refer to the SAP for more details.
5. Comparison between baricitinib and placebo in mean severity of morning joint stiffness in the 7 days prior to Week 12: An ANCOVA model with treatment, country, joint

erosion status, and baseline score (Day 1 on the diaries) in the model will be used to test the treatment difference between baricitinib and placebo in mean severity of morning joint stiffness in the 7 days prior to Week 12. Refer to the SAP for more details.

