5.2. Determination of Sample Size

Approximately 288 patients (144 in baricitinib, 144 in placebo) will provide:

- 99% power to detect a difference between the baricitinib and placebo treatment groups in ACR20 response rate (60% versus 35%) at Week 12 based on a 2-sided chi-square test at a significance level of 0.05.

The sample size and power estimates were obtained using nQuery® Advisor 7.0.

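### The Week 1 diary window takes in diary Day 1, so by-visit Week 1 estimates are diluted by about 14% for an on-time visit (minor)

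*SAP*

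**What the plan says.** SAP 6.13.1.1 has the paper diary completed daily from Visit 2 to Visit 7 and bases the main analysis on the average over the seven days before the Week 12 visit. It then carries the method to earlier visits: "Similar analysis will be done for 7 days prior to each scheduled visit (Week 1, Week 2, Week 4, and Week 8"). If a window holds fewer than four scores, it is moved back one day at a time towards baseline.

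The supportive analysis in the same section uses fixed diary weeks and keeps Day 1 apart: "Day 1 on diary, Days 2-8 (Week 1), Days 9-15 (Week 2"), and so on to Days 79-85 for Week 12.

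Day 1 is the baseline. Protocol 12.2.7 puts the "baseline score (Day 1 on the diaries) in the model". SAP 6.13.1.2 keeps Day 1 as the covariate for stiffness severity, and analyses worst tiredness and worst joint pain in the same manner. For stiffness duration the SAP replaces ANCOVA with the Hodges-Lehmann estimate and Wilcoxon test on the averages, with no baseline term.

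The protocol's study schedule (Attachment 1) puts Visit 3 at 7 ± 2 days after Visit 2.

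**The concern.** A visit-based seven-day window works when at least seven post-baseline diary days precede the visit. At Week 1 they do not: only Days 2-7 lie between Day 1 and an on-time Visit 3, so the seventh day is Day 1. For three measures the same score then sits on both sides of the model. For all four, one of the averaged days is a baseline day.

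The Week 1 difference is therefore pulled towards zero by an amount set by visit timing. The main and supportive analyses would also report Week 1 on different days. What is at stake is the first point of the by-visit diary profile; Week 1 is not itself a named endpoint.

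**Working it through.** **The plan's own power figure.** SAP 5.2 states "99% power to detect a difference between the baricitinib and placebo treatment groups in ACR20 response rate (60% versus 35%) at Week 12", with 144 per arm, "based on a 2-sided chi-square test at a significance level of 0.05". With a pooled rate of 0.475:

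z = [0.25 × √144 − 1.96 × √(2 × 0.475 × 0.525)] / √(0.60 × 0.40 + 0.35 × 0.65) = (3 − 1.384) / 0.684 = 2.36, so power = 0.991.

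The stated 99% is reproduced. It concerns ACR20 only; no size or power is given for any diary measure.

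**Diary calendar.** Visit 7 is 84 days after Visit 2. With Visit 2 as Day 1, Visit 7 is Day 85, which agrees with the SAP's label of Days 79-85 for Week 12. On the same count an on-time Visit 3 is Day 8, and the allowed range is Days 6 to 10.

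**Weight of Day 1 in the Week 1 average** (complete diary, window ending the day before the visit):

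| Visit 3, days after Visit 2 | Diary days averaged | Weight of Day 1 | Estimate relative to the average without Day 1 |
|---|---|---|---|
| +5 | 1-5 | 1/5 | 0.80 (20% too small) |
| +6 | 1-6 | 1/6 | 0.833 (17%) |
| +7 | 1-7 | 1/7 | 0.857 (14%) |
| +8 | 2-8 | 0 | 1 |
| +9 | 3-9 | 0 | 1 |

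If only four scores are present and Day 1 is one of them, its weight is 1/4 (25%).

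**Three rating scales (ANCOVA on Day 1).** For an on-time visit, mean(Days 1-7) = (1/7) × Day 1 + (6/7) × mean(Days 2-7). Day 1 is already in the model, so the first term changes only the covariate slope. The treatment coefficient and its standard error are both multiplied by 6/7, and the t statistic does not move. One simulated trial (144 per arm, assumed SD 2, within-patient correlation 0.7, effect growing from 0.2 to 0.65 points) confirms this:

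- Days 1-7: −0.357 (SE 0.105), p = 0.00073.
- Days 2-7: −0.417 (SE 0.122), p = 0.00073.

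The identity is exact with complete diaries and a common visit day. With mixed visit days the p-value is only approximately unchanged.

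**Duration (no baseline term).** The documents give no SD, correlation or daily effect, so these are assumptions: normal scores with SD 2, no effect on Day 1, then either a constant 0.5 or the growing effect above; 1,500 trials per scenario.

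| Effect | Correlation | Power, Days 1-7 | Power, Days 2-7 |
|---|---|---|---|
| Constant | 0.5 | 0.64 | 0.77 |
| Constant | 0.7 | 0.55 | 0.69 |
| Constant | 0.9 | 0.44 | 0.58 |
| Growing | 0.5 | 0.50 | 0.64 |
| Growing | 0.7 | 0.41 | 0.52 |
| Growing | 0.9 | 0.35 | 0.46 |

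The Hodges-Lehmann shift is about 0.86 of the Days 2-7 value throughout, and power falls by roughly 10 to 14 points. Real durations are skewed and truncated at 720 minutes, so the power figures are illustrative.

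**Other visits.** For on-time visits the Week 2 window is Days 8-14 and the Week 12 window is Days 78-84. Neither contains Day 1 unless it is moved back for missing scores.

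**The case against.** The best defence is that the section already treats Day 1 as separate. It labels Days 2-8 as Week 1, and its fallback rule speaks of post-baseline windows, so a programmer might leave Day 1 out unprompted. That shows probable intent, but it does not settle the rule. No full post-baseline week precedes an on-time Visit 3, so the main method either includes Day 1 or has no seven-day window at Week 1. Counting the visit day as prior would give Days 2-8 for an on-time visit, but Day 1 would still enter for early ones (1/7 at +6, 1/6 at +5). Diary entries are also made at the end of the day, normally after the visit.

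The remaining objections limit the point and stand:

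- The overlap is not universal. Visits at +8 and +9 days are allowed and give clean windows.
- It would be wrong to say that Day 1 is both baseline and outcome for all four measures; duration has no Day 1 term in its main SAP analysis.
- The by-visit repeat is written out for duration, severity and tiredness. For joint pain it rests on the general sentence alone.
- Week 1 diary results are neither secondary endpoints nor listed exploratory objectives, and the shrinkage is conservative.

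**Conclusion.** The point holds as a minor defect. Read plainly, SAP 6.13.1.1 averages diary Day 1 into the Week 1 outcome for on-time and early visits. With complete diaries, the estimate and interval are too small by 14% on time, 17% one day early and 20% two days early, and by nothing one or two days late. The overall dilution depends on the distribution of visit dates, which the documents do not give. The result rests on the window ending the day before the visit and on Day 1 carrying no drug effect. The rating-scale tests are essentially unchanged, duration loses some power, and the Week 12 secondary endpoints are not affected by the overlap.

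A reader might go further. "At Visit 2 (Week 0), patients will take their investigational product in the clinic", while "Items being measured using a paper diary should be completed at the end of the" day, so the Day 1 tiredness and pain scores could be called post-dose covariates that bias Week 12. The documents do not support that step. SAP 6.1.1 defines the efficacy baseline value by date, up to and including the date of first dose, and a Day 1 entry meets it. The protocol names Day 1 as the covariate. The recall is the worst level over 24 hours, which includes hours before the dose. No document gives a Day 1 drug effect from which to size a bias. Nor is there a case for substituting the Visit 2 tablet score: no passage says the tablet is completed before the dose.

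**What to change.** Add to SAP 6.13.1.1, in substance: *No outcome window, including one shifted back for missing scores, may include diary Day 1. The Week 1 window is diary Days 2-8, with at least four non-missing scores required.*

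Days 2-8 is preferable to running from Day 2 to the day before Visit 3, which would give eight days at +9 and only four at +5. The diary continues daily to Week 12, so Days 2-8 can be filled even when Visit 3 is early. The shift-back wording is needed because a Week 2 or later window with few scores could otherwise reach Day 1. The text should also say that a patient with fewer than four scores in Days 2-8 falls under the section's existing rule of carrying Day 1 forward, since no earlier window remains.

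The cost is two sentences in the SAP and no new data. The main and supportive analyses would then use the same Week 1 days. The covariates stay as planned. The protocol specifies diary analyses only for Week 12, so this change does not touch its text.
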